| IDeg | insulin degludec |
| IDF | International Diabetes Federation |
| ITT | intention-to-treat |
| LDL | low density lipoprotein |
| LLOQ | lower limit of quantification |
| LOCF | Last Observation Carried Forward |
| MACE | major adverse cardiovascular event |
| MAP | modelling analysis plan |
| MCMC | Markov Chain Monte Carlo |
| MedDRA | Medical Dictionary for Regulatory Activities |
| MMRM | mixed model for repeated measurements |
| OAD | oral antidiabetic drug |
| PK | pharmacokinetics |
| PP | per protocol |
| SAP | statistical analysis plan |
| SAS | safety analysis set |
| SD | standard deviation |

SU sulphonylureas
T2DM type 2 diabetes mellitus
TEAEs treatment emergent adverse events
TTT treat-to-target
TZD thiazolidinedione
UNR upper normal range
UTN Universal Trial Number
VLDL very low density lipoprotein

1 Introduction

1.1 Trial information

This is a 26 week, randomised, parallel three-arm, open-label, multi-centre, treat-to-target (TTT) confirmatory trial in Chinese subjects with T2DM inadequately controlled with metformin \pm one other OAD: α -glucosidase inhibitors (AGI), sulphonylureas (SU), glinides and thiazolidinediones (TZD). The trial is comparing efficacy and safety of insulin degludec/liraglutide (IDegLira), insulin degludec (IDeg) and liraglutide, all in combination with Metformin. For further details please see the protocol.

1.2 Scope of the statistical analysis plan

This Statistical Analysis Plan (SAP) is based on final Protocol version 5.0 (05-Dec-2016). The scope of this SAP is to add one sensitivity analysis for change from baseline in HbA_{1c} after 26 weeks of treatment and several sensitivity analyses for confirmatory secondary endpoints, and to perform other minor changes. For further details on the changes see section [3](#).

2 Statistical considerations

Novo Nordisk will analyse and report data from all sites together.

All analyses of efficacy and safety endpoints will be based on the full analysis set (FAS). The analysis of the primary endpoint and the confirmatory secondary endpoint, change from baseline in body weight after 26 weeks of treatment, will be repeated on the per-protocol (PP) analysis set and the completer analysis set (CAS) for sensitivity purposes. All efficacy endpoints will be summarised using the FAS and safety endpoints will be summarised using the safety analysis set (SAS).

The impact of protocol deviations and outliers may be investigated further in sensitivity analyses if deemed relevant.

Unless otherwise specified, all continuous measurements will be summarised descriptively at each visit by treatment using observed data. After 26 weeks of treatment, descriptive statistics will be presented based both on observed and last observation carried forward (LOCF) imputed data. Endpoints that are analysed untransformed and endpoints that are not formally analysed are summarised by the arithmetic mean, standard deviation (SD), median, and minimum and maximum value. Endpoints that are analysed log-transformed are summarised by the geometric mean and coefficient of variation (CV).

For measurements over time, mean values will be plotted to explore the trajectory over time. LOCF imputed data will be used as the basis for plotting data, if not otherwise specified. For endpoints that are analysed log-transformed, the geometric mean values will be plotted.

A standard analysis of covariance (ANCOVA) model will be applied for the continuous primary and secondary endpoints. The model includes treatment and previous OAD treatment (metformin or metformin in combination with one other OAD) as fixed factors and the corresponding baseline value as covariate. In the following, this model will be referred to as the standard ANCOVA model.

Presentation of results from a statistical analysis will include the estimated mean treatment effects (Least Square Means [LSMeans]) for absolute values and change from baseline. In addition, estimated mean treatment difference (or ratio) will be presented together with the two-sided 95% confidence interval and corresponding two-sided p-value.

Handling of missing data

The expected percentage of missing data is around 15%. In accordance with industry guidance¹ endpoints will be assessed at frequent visits and also on subjects who withdraw prematurely. This will facilitate an analysis in accordance with ITT principles. Also, the combined information on frequent outcomes and information on reason for drop-out is assumed to account for the missing data anticipated.

If an assessment has been made both at screening (Visit 1) and randomisation (Visit 2), and if not otherwise specified, the value from the randomisation visit will be used as the baseline value. If the value measured at the randomisation visit is missing and the assessment also has been made at screening, then the screening value will be used as the baseline value.

Missing values (including intermittent missing values) will be imputed using the LOCF method. Subjects without data after randomisation will be included by carrying forward their baseline value. LOCF has been a standard approach in diabetes trials for many years, and was used as the primary analysis in both IDegLira and IDeg phase 3a trials. LOCF is considered to be an appropriate method in the context of TTT trials, where subjects after withdrawal typically continue their therapy using commercially available insulin. In previous TTT trials with IDegLira and IDeg, LOCF has generally provided similar results to alternative methods applied to handle missing data, such as repeated measures models and completer analyses. In this trial, similar sensitivity analyses will be made to examine the robustness of the LOCF method. The LOCF approach will also be used to impute missing values in CAS.

2.1 Sample size calculation

The primary objective of this trial is to confirm the efficacy of IDegLira in controlling glycaemia as assessed by change from baseline in HbA_{1c} after 26 weeks of treatment vs. IDeg and liraglutide, respectively. This is done by comparing the difference in change from baseline in HbA_{1c} after 26 weeks of treatment to a non-inferiority margin of 0.4% for IDegLira vs. IDeg and to a superiority margin of 0.0% for IDegLira vs. liraglutide. The non-inferiority margin of 0.4% (absolute) was chosen in accordance with the FDA guidance¹.

A hierarchical testing procedure is applied. This is based on an a priori ordering of the null-hypotheses and testing them in this order using the two-sided 95% confidence interval approach until an insignificant result appears. Non-inferiority and superiority will thus be considered confirmed if the upper bound of the two-sided 95% confidence interval is below 0.4% and 0.0%, respectively. This is equivalent to using a one-sided test of size 2.5%, which means that the type 1 error rate is controlled at 2.5% (one-sided).

Formally, let D be the mean difference in change from baseline in HbA_{1c} . The null-hypotheses are given as:

- Non-inferiority: $H_0 D \geq 0.40\%$ against $H_A D < 0.40\%$, with an assumed mean difference in treatment of 0.0% and a standard deviation of 1.0%
- Superiority: $H_0 D \geq 0.0\%$ against $H_A D < 0.0\%$, with an assumed mean difference in treatment of -0.3% and a standard deviation of 1.0%

For evaluation of non-inferiority the PP-population is used for the sample size calculations, while the FAS is used for evaluation of superiority. It is assumed that 15% of the randomised subjects will be excluded from the PP analysis set. The above assumptions are based on experience from the phase 3a development programmes for IDegLira and IDeg. The sample size is determined using a t-statistic under the assumption of a one-sided test of size 2.5% for both the superiority and non-inferiority testing. Based on these assumptions a sample size of 720 patients results in a non-inferiority power of 98.1% and a superiority power of 90.7% i.e. the combined power for meeting the primary objective is $98.1\% * 90.7\% = 89.0\%$. A sample size of 720 patients with a 15% drop-out rate and a 2:1:1 randomisation results in 306 PP patients in the IDegLira arm.

2.2 Definition of analysis sets

The following analysis sets are defined in accordance with the ICH-E9 guidance².

- **Full Analysis Set (FAS):** includes all randomised subjects. In exceptional cases, subjects may be eliminated from the full analysis set. In such cases the elimination will be justified and documented. The statistical evaluation of the FAS will follow the intention-to-treat (ITT) principle and subjects will contribute to the evaluation “as randomised”.
- **Per-Protocol (PP) analysis set:** includes all subjects in the FAS who fulfils the following criteria:
 - Have not violated any inclusion criteria
 - Have not fulfilled any exclusion criteria
 - Have a non-missing HbA_{1c} at screening or randomisation
 - Have at least one non-missing HbA_{1c} after 12 weeks of exposure
 - Have at least 12 weeks of exposure

Subjects will contribute to the evaluation “as treated”.

- **Safety Analysis Set (SAS):** includes all subjects receiving at least one dose of the investigational product or comparator. Subjects in the safety set will contribute to the evaluation “as treated”.
- **Completer Analysis Set (CAS):** includes all randomised subjects who have completed the trial. Subjects in the completer analysis set will contribute to the evaluation “as randomised”.

Randomised subjects who are lost to follow up and where no exposure information of the investigational product or comparators is available after randomisation will be handled as unexposed.

Before data are released for statistical analysis, a review of all data will take place to identify protocol deviations that could potentially affect the results. Any decision to exclude any subject or observation from the statistical analysis is the joint responsibility of the members of the study group. The subjects or observations to be excluded, and the reasons for their exclusion must be documented and signed by those responsible before database lock. The subjects and observations excluded from analysis sets, and the reason for this, will be described in the clinical trial report.

2.3 Primary endpoint

The primary endpoint is defined as change from baseline in HbA_{1c} after 26 weeks of treatment.

The change from baseline in HbA_{1c} after 26 weeks of treatment will be analysed using an ANCOVA model with treatment and previous OAD treatment (metformin ± one other OAD) as fixed factors and baseline HbA_{1c} as covariate. Missing values after 26 weeks of treatment will be imputed applying LOCF using HbA_{1c} values at and after baseline.

Non-inferiority of IDegLira vs. IDeg will be considered as confirmed if the 95% confidence interval for the mean treatment difference lies entirely below 0.4%; equivalent to a one-sided test with significance level of 2.5%. Non-inferiority will be investigated on the FAS. Sensitivity analysis will be performed on the PP analysis set.

Superiority of IDegLira vs. liraglutide will be considered as confirmed if the 95% confidence interval for the mean treatment difference for change from baseline in HbA_{1c} lies entirely below 0.0%; equivalent to a one-sided test with significance level of 2.5%. Conclusion of superiority will be based on FAS. The primary objective will be fulfilled only if both non-inferiority of IDegLira vs. IDeg and superiority of IDegLira vs. liraglutide are confirmed.

In addition to the non-inferiority margin of 0.4% the upper bound of the confidence interval for the mean treatment difference of IDegLira vs. IDeg will also be compared to a 0.0% margin. This comparison is not part of the hierarchical testing procedure.

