2.4 Secondary endpoints

2.4.1 Confirmatory secondary endpoints

The following two confirmatory endpoints will be tested for superiority of IDegLira vs. IDeg.

- Change from baseline in body weight after 26 weeks of treatment.
- Number of treatment emergent severe or BG confirmed hypoglycaemic episodes during 26 weeks of treatment.

The tests for superiority of the confirmatory secondary endpoints will be based on the FAS and will only be carried out if non-inferiority of IDegLira vs. IDeg and superiority of IDegLira vs. liraglutide with regards to the primary endpoint are confirmed.

In order to control the overall type I error on a 2-sided 5% level with regards to the secondary endpoints, a hierarchical testing procedure will be used. If superiority is confirmed with respect to change from baseline in body weight after 26 weeks of treatment the number of treatment emergent severe or BG confirmed hypoglycaemic episodes during 26 weeks of treatment will be tested for superiority.

Superiority for change from baseline in body weight will be considered confirmed if the upper bound of the two-sided 95% confidence interval for the estimated mean treatment difference (IDegLira minus IDeg) is strictly below zero or equivalently if the p-value for the one-sided test of

$$H_0 D \geq 0.0 \text{ against } H_A D < 0.0,$$

is less than 2.5%, where D is the treatment difference.

The change from baseline in body weight after 26 weeks of treatment will be analysed using an ANCOVA model with treatment and previous OAD treatment (metformin ± one other OAD) as fixed factors and baseline weight as covariate.

Similar sensitivity analyses as specified for the primary endpoint (ANCOVA on the PP analysis set and CAS; MMRM; the pattern mixture model similar to that described for HbA_{1c}, but without added non-inferiority penalty) will be performed.

Superiority for hypoglycaemic episodes will be considered confirmed if the upper bound of the two-sided 95% confidence interval for the estimated mean treatment ratio (IDegLira vs. IDeg) is strictly below one or equivalently if the p-value for the one-sided test of

$$H_0 \text{ RR} \geq 1.0 \text{ against } H_A \text{ RR} < 1.0,$$

is less than 2.5%, where RR is the treatment rate ratio.

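### The HbA1c comparison of IDegLira with IDeg against 0.0% sits outside the test hierarchy and can only be supportive; a pre-specified last step would have cost no other test anything

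*SAP*

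**What the plan says.** Section 2.1 sets the primary objective as two HbA1c comparisons, against "a non-inferiority margin of 0.4% for IDegLira vs. IDeg and to a superiority margin of 0.0% for IDegLira vs. liraglutide". Hypotheses are ordered in advance, "testing them in this order using the two-sided 95% confidence interval approach until an insignificant result appears", and the section states the consequence: "This is equivalent to using a one-sided test of size 2.5%, which means that the type 1 error rate is controlled at 2.5% (one-sided").

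Section 2.3 requires both comparisons to succeed. It then adds a further look at the IDegLira-IDeg interval, against 0.0%, and gives its status: "This comparison is not part of the hierarchical testing procedure". It does not use the language of confirmation that it uses for the two primary tests, and it does not call the comparison supportive or exploratory.

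Section 2.4.1 opens the secondary tests only after both primary tests have succeeded. There "a hierarchical testing procedure will be used": body weight first, then the number of severe or BG confirmed hypoglycaemic episodes, both for superiority over IDeg. The sequence ends there.

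For planning, section 2.1 works on the IDeg comparison "with an assumed mean difference in treatment of 0.0% and a standard deviation of 1.0" per cent, and on the liraglutide comparison "with an assumed mean difference in treatment of -0.3% and a standard deviation of 1.0" per cent.

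**The concern.** The plan gives superiority over IDeg confirmatory status for body weight and hypoglycaemia but not for HbA1c, the primary endpoint, although it intends to look at whether that interval lies below zero. The SAP gives no reason. If the trial finds better glycaemic control than with IDeg, that finding stands outside the multiplicity-controlled set, however large it is.

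A hypothesis placed at the end of a fixed sequence takes nothing from the hypotheses before it. The plan therefore gave up a possible confirmatory conclusion without gaining alpha or power elsewhere. A smaller matter is that section 2.3 says what the comparison is not, without saying what it is.

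**Working it through.** **Inputs (SAP section 2.1).** One-sided alpha 2.5%; SD 1.0%; 720 subjects randomised 2:1:1, so the FAS has 360/180/180. On the PP set, "It is assumed that 15% of the randomised subjects will be excluded from the PP analysis set", which leaves 720 × 0.5 × 0.85 = 306 and 720 × 0.25 × 0.85 = 153 per comparator.

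**1. The plan's own figures.** Power comes from the noncentral t distribution, with noncentrality = distance / (SD × √(1/n₁ + 1/n₂)).

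- Non-inferiority on PP: √(1/306 + 1/153) = 0.0990; 0.4 / 0.0990 = 4.04; power 98.1% (SAP: 98.1%).
- Superiority over liraglutide on FAS: √(1/360 + 1/180) = 0.0913; 0.3 / 0.0913 = 3.29; 538 degrees of freedom; power 90.7% (SAP: 90.7%).
- Combined: 0.981 × 0.907 = 0.890 (SAP: 89.0%).

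The figures reproduce.

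**2. Error control with an added last step.** The order would be: non-inferiority vs IDeg, superiority vs liraglutide, body weight, hypoglycaemia, HbA1c superiority vs IDeg. Take the first true null hypothesis in that order. No later null can be rejected unless this one is, and it is rejected with probability at most 2.5%. Familywise error is therefore at most 2.5%, whatever follows. Steps 1 to 4 are decided before step 5 is reached, so their error rates and power do not change.

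A simulation of 2,000,000 trials per setting agrees (FAS sizes, shared IDegLira arm, secondary endpoints as normal test statistics):

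| True state | Listed hypotheses only | With the added last step |
|---|---|---|
| HbA1c difference 0 vs IDeg, large benefit vs liraglutide, no effect on weight or hypoglycaemia | 2.48% | 2.48% |
| As above, but strong effects on weight and hypoglycaemia | 0% (no listed null is true) | 2.49% |

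The largest value over all settings tried was 2.52%. The simulation standard error is √(0.025 × 0.975 / 2,000,000) = 0.011 percentage points, so this agrees with 2.5%.

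**3. What the added step could deliver.** Marginal power on the FAS, 360 vs 180, SD 1.0%:

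| True IDegLira minus IDeg | Noncentrality | Power |
|---|---|---|
| 0.0% (the SAP's assumption) | 0 | 2.5% |
| -0.1% | 1.10 | 19% |
| -0.2% | 2.19 | 59% |
| -0.3% | 3.29 | 90.7% |

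The chance of reaching and winning the step cannot exceed these figures, because body weight and hypoglycaemia must be won first. The SAP gives no power for either. As an illustration only: with a true difference of -0.3% against both comparators and both secondary tests nearly certain to succeed, the simulated chance of reaching and winning step 5 is about 84%.

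**4. The results already attached.** Output table 2 gives IDegLira minus IDeg as -0.5947 with standard error 0.06819 and a 95% CI of -0.7286 to -0.4608. The upper bound is below 0.0%, so the outcome of the proposed step is already known.

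**The case against.** The strongest case against is that nothing here is wrong. The exclusion is stated openly, section 2.4.1 names only two confirmatory secondary endpoints, and the SAP makes no confirmatory claim for HbA1c superiority over IDeg. Leaving the test out also fits a treat-to-target plan that assumed no HbA1c difference from IDeg: under that assumption the extra test would succeed only 2.5% of the time. All of this stands, and it limits the point to a design suggestion.

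A reader might go further in three ways that the SAP does not support.

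- **That the plan inflates type I error.** If the 0.0% comparison were claimed beside the secondary sequence, two 2.5% tests would run in parallel, and familywise error could approach 1 - 0.975² = 4.94% one-sided (4.91% in simulation). Section 2.3 rules out that reading by placing the comparison outside the hierarchy. The plan as written has no inflation.
- **That power for the extra test was 90.7%.** That figure belongs to a difference of -0.3%, which the SAP assumes against liraglutide and not against IDeg.
- **That the trial cannot address the question with any error control.** The single two-sided 95% interval has 2.5% one-sided error for that one comparison. What it lacks is familywise protection alongside the secondary tests.

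It could also be said that the output already treats the comparison as supportive, since table 7 repeats the HbA1c analysis of table 2 under a supportive label. The output does not link table 7 to the 0.0% comparison, so this is suggestive only.

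**Conclusion.** The point holds as a missed opportunity. The HbA1c comparison of IDegLira with IDeg against 0.0% has no place in the hierarchy, so a favourable result is supportive. Control at one-sided 2.5% for the hypotheses the SAP lists is unaffected.

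Adding the comparison last would have kept familywise error at 2.5% at no cost to any other test. The benefit would have been small near the planning assumption of no difference and substantial from about -0.2% onwards, provided both secondary tests succeeded. These figures rest on SD 1.0%, the FAS sizes of 360 and 180, and fixing the step before data were seen.

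The last condition can no longer be met. A reader might infer from the attached interval, which lies well below zero, that superiority over IDeg is confirmed, or that it could be made so by amending the hierarchy now. Neither follows: a step added with its result in view is post hoc.

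**What to change.** **As a plan, before data are seen.** In section 2.3, replace the sentence that excludes the comparison with a pointer to section 2.4.1. In section 2.4.1, add: *If superiority is confirmed for body weight and then for the number of hypoglycaemic episodes, superiority of IDegLira vs IDeg in change from baseline in HbA1c is tested last, on the FAS, at one-sided 2.5%. If any earlier step fails, the comparison is supportive.* This is two sentences, with no change to the alpha or power of any existing test. Section 3 lists no change to the hierarchy, so it was presumably carried over from protocol version 5.0; in that case the protocol would need the same amendment.

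**For this completed trial.** Leave the hierarchy as it is. State in the report that the comparison with 0.0% is supportive and carries no confirmatory superiority claim, and present the estimate with its 95% interval on that footing. The cost is one sentence.

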2.3.1 Sensitivity analysis

The primary analysis will be repeated on the PP analysis set and the CAS as sensitivity analysis. Furthermore, sensitivity analysis will be performed on FAS using the mixed model for repeated measurement (MMRM) to evaluate the sensitivity of using LOCF. All HbA_{1c} values available post baseline at scheduled measurement times will be analysed in a linear mixed normal model using an unstructured residual covariance matrix for HbA_{1c} measurements within the same subject. The model will include treatment, visit, and previous OAD treatment as fixed factors and baseline HbA_{1c} as covariate. Interactions between visit and all factors and the covariate are also included in the model.

Further, a pattern mixture model approach, mimicking an ITT scenario will be applied. The imputation will follow the hypothesis being tested. i.e., when deriving the IDegLira vs. IDeg contrast the imputation in the IDegLira arm will be based on IDeg values, whereas for the IDegLira vs. liraglutide contrast the imputation in the IDegLira arm will be based on liraglutide values. Furthermore, 0.4% (absolute) will be added to the imputed values in the IDegLira arm for the non-inferiority comparison against IDeg to mimic a scenario where subjects discontinued from IDegLira treatment are assumed to be switched to a treatment inferior to IDeg. In other words: two imputation datasets will be made, one for IDegLira and IDeg and one for IDegLira and liraglutide. In the analyses, depending on the hypothesis being tested, the respective imputation dataset will be used and the third arm (from the other imputation dataset) will be kept in the model. The imputations for each hypothesis will be done as follows:

- In the first step intermittent missing values are imputed using a Markov Chain Monte Carlo (MCMC) method, in order to obtain a monotone missing data pattern. This imputation is done for each treatment group separately and 1000 copies of the dataset will be generated.
- In the second step, for each of the 1000 copies of the dataset, an analysis of variance model with previous OAD treatment as a fixed factor, and baseline HbA_{1c} as a covariate is fitted to the change in HbA_{1c} from baseline to 4 weeks (Visit 6) for a given comparator group only. The estimated parameters, and their variances, from this model are used to impute missing values at 4 weeks for subjects in the comparator and IDegLira treatment groups, based on previous OAD treatment and HbA_{1c} at baseline.
- In the third step, for each of the 1000 copies of the dataset, missing HbA_{1c} values at 8 weeks (Visit 10) are imputed in the same way as for 4 weeks. Now the imputations are based on an analysis of variance model with the same factors and the HbA_{1c} values at baseline and 4 weeks as covariates, fitted to the comparator group.
- This stepwise procedure is then repeated sequentially over the available planned visits, adding one visit in each step until the last planned visit at 26 weeks (Visit 28).

- For the comparison against IDeg, for each subject discontinued from treatment in the IDegLira treatment group, a value of 0.4% (absolute; the non-inferiority limit) is added to the change in HbA_{1c} at 26 weeks.

For each of the complete data sets, the change from baseline to 26 weeks is analysed using an analysis of variance model with treatment and previous OAD treatment as fixed factors and baseline HbA_{1c} value as a covariate.

The estimates and standard deviations for the 1000 data sets are pooled to one estimate and associated standard deviation using Rubin's rule³. From these pooled estimates the confidence interval for the treatment differences and the associated p-value are calculated.

The results of sensitivity analyses will be compared to the result of the standard ANCOVA method using LOCF for imputation of missing data. Any marked difference between the MMRM, the pattern mixture approach and ANCOVA LOCF approach regarding the estimated treatment difference will be commented upon in the CTR.

